9. STATISTICAL CONSIDERATIONS

9.1. General Design Issues

This study will be conducted as a parallel group randomized clinical trial. The main goal is to define if Smartheart 12 lead ECG home device will decrease the rates of ED visits and rehospitalization in patients after index hospitalization for acute MI.

Our central primary hypothesis is that the Smartheart 12 lead ECG home device will decrease the ED visits and rehospitalization rates, leading to subsequent decrease in healthcare costs. Additional potential benefit is decrease in mortality by identifying any cardiac emergency at the early stage with appropriate urgent medical assistance. The quality of life of patients with the Smartheart device at home could be improved, knowing there is an easily available tool which can provide quick and reliable diagnosis.

9.2. Sample Size and Randomization

Patients will be randomized to either standard medical therapy or the medical therapy plus the Smartheart 12 lead ECG home device.

The primary combined endpoint parameter is the rate of ED visits/rehospitalizations as well as related downstream cardiovascular testing (echocardiogram, stress test or coronary CT, or invasive coronary angiogram) at 90 (+/-7) days after discharge and mortality rates during the 90 (+/-7) days of follow up. Based on the most recent in-house registry data, we have about 50 AMI patients undergoing PCI a month. Accordingly, we have at least 600 patients a year who are discharged with a diagnosis of AMI from Saint Mary's Hospital.

Our own registry data further indicate that 24% of revascularized AMI patients will present to the ED or will be readmitted within 90 days. This is in keeping with the published literature citing a rate of 20-30%. Half of these patients will present for cardiovascular complaints and may get further testing, including echocardiogram, stress test or coronary CT, or invasive coronary angiogram. Having a 12-lead ECG available and the phone triage available to direct care may impact not only emergency presentation but also downstream testing. This will be considered in this trial, and each of these will be considered as a component to the combined primary endpoint event. Assuming that patients presenting with cardiovascular concern may receive two of the outlined downstream test as they present to the ED and hospital, the estimated event rate will be 48%. With 120 patients in each arm the study we would be adequately powered (beta error <0.2) to show a statistically significant (at alpha error levels of <0.05) for a 37.5% event reduction.

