9.4. Interim Analyses and Stopping Rules

Due to the uncertainty in proposed rehospitalization rate of the treatment arm, a sample size reestimation (SSR) will be performed after 60 patients have finished the study in the treatment group. The rate will be estimated only for the treatment group, and the sample size will be recalculated using the new calculated rate. The results of this calculation will be the new larger sample size for the study. If the calculation proposes a sample size that is smaller, the original 120 patients per group will be used. No stopping rules are implemented for this pilot study.

As an example, there may be more rehospitalizations and ER visits than expected in the treatment group. If the rehospitalizations and ER visits were 17.5% at 90 days, this would result in the sample size being increased to 181/group. Alternatively, if the rehospitalizations and ER visits in the treatment group were 10%, the sample size required would only be 62/group. If this were to happen, the sample size for the study would be maintained at 120 per group.

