9.5.1.1. Primary outcome measures

The combined primary endpoint of the trial is the rate of ED visits, hospital readmission, and any of the downstream testing modalities (echocardiogram, stress test or coronary CT, or invasive coronary angiogram) from discharge after index hospitalization for MI to 90 days of follow-up between group 1 and group 2.

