9.6. Data Analyses

The primary analysis for Aim 1 (lead aim of the study) will be a comparison of the rates of the primary combined endpoint between group 1 and 2 via Chi square test for categorical data of independent samples. The test will be used for any other categorical data. For continuous data, an independent groups t-test or Wilcoxon as appropriate after testing distributional assumptions.

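### The 48% control rate in section 9.2 counts events, but the chi-square test counts patients; at the plan's 24% per patient, 120 per arm gives about 43% power, and section 9.4 as written does not restore 80%

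*Combined protocol and SAP*

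**What the plan says.** Section 9.2 takes from the site's registry that "24% of revascularized AMI patients will present to the ED or will be readmitted within 90 days" and gives a published range of 20-30%. It says half of these patients present with cardiovascular complaints, assumes two downstream tests for each, and places the tests at the presentation itself: "as they present to the ED and hospital, the estimated event rate will be 48" per cent. It then states: "With 120 patients in each arm the study we would be adequately powered (beta error <0.2"), meaning power to find a result "statistically significant (at alpha error levels of <0.05) for a 37.5% event reduction".

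Section 9.5.1.1 defines the primary endpoint as ED visits, readmission and "any of the downstream testing modalities (echocardiogram, stress test or coronary CT, or invasive coronary angiogram"). Section 9.2 also adds mortality. Section 9.6 compares the rates of the combined endpoint "via Chi square test for categorical data of independent samples".

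Section 9.4 re-estimates the sample size after 60 treatment-group patients have finished. Only the treatment-group rate is updated, and 120 per group is the minimum. No control rate and no maximum are given. Its two examples are: "If the rehospitalizations and ER visits were 17.5% at 90 days, this would result in the sample size being increased to 181/group"; and "if the rehospitalizations and ER visits in the treatment group were 10%, the sample size required would only be 62/group".

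**The concern.** A chi-square test for independent samples needs each patient to be counted once, with or without an event. A patient who comes to the ED and has two tests there contributes three events to the 48 but only one patient to the test. If 48% is a count of events, the power calculation has been fed a rate about twice the per-patient rate that the plan supports.

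A non-significant result would then be read as coming from a trial with at least 80% power when the real figure may be about half that. The re-estimation is meant to protect against a wrong rate, but it updates only the treatment group. Whether it helps depends on a control rate that section 9.4 does not state.

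**Working it through.** **Inputs.** From section 9.2: 24% with an ED visit or readmission; half of these (12% of all patients) cardiovascular; two tests each; 120 per arm; alpha 0.05; beta below 0.2; 37.5% reduction. From section 9.3: 1:1 allocation. Assumptions: two-sided test (sidedness is not stated), no dropout.

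**Formula.** With p̄ = (p1 + p2)/2, s0 = √[2p̄(1 − p̄)] and s1 = √[p1(1 − p1) + p2(1 − p2)]:

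- n per arm = (1.960·s0 + 0.842·s1)² / (p1 − p2)²
- power = Φ{[|p1 − p2|·√n − 1.960·s0] / s1}

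**1. The plan's own figure.** The reduced rate is 0.48 × 0.625 = 0.30. Then s0 = 0.690, s1 = 0.678 and n = 114.1, so 115 per arm. Power at 120 per arm is 82.0% (83% by exact enumeration). The claim in 9.2 reproduces, provided 48% is a proportion of patients.

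**2. Where 48% comes from.** The protocol does not print the sum, but 0.24 + 2 × 0.12 = 0.48 matches exactly. The other possible route, 2 × 0.24, also counts events. The tests belong to patients already in the 24%, so on this derivation the per-patient rate is 24%.

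**3. Power at the per-patient rate.** The reduced rate is 0.24 × 0.625 = 0.15. Then s0 = 0.560, s1 = 0.557 and n = 303.04, so 304 per arm. Power at 120 per arm is 42.0% (42.6% exact). The 95% CI half-width for the difference is 1.96 × √[(0.24 × 0.76 + 0.15 × 0.85)/120] = 0.0996, about 10 percentage points. At 24%, 120 per arm has 80% power only for a fall to about 10.4%, a reduction of 1 − 10.4/24 = 57%.

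**4. Other per-patient control rates** (120 per arm, 37.5% reduction):

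| Control rate | Power |
|---|---|
| 20% | 35% |
| 24% | 42-43% |
| 30% | 53% |
| 35% | 62% |
| 40% | 70% |
| 46.5% | 80% |
| 48% | 82% |

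**5. The control rate behind section 9.4.** Required n per group for its two example treatment rates, by control rate:

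| Control rate | Treatment 17.5% | Treatment 10% |
|---|---|---|
| 24% | 610 | 112 |
| 30% | 181 (180.8) | 62 (61.6) |
| 48% | 36 | 22 |
| Section 9.4 states | 181 | 62 |

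Only 30% reproduces both examples. The 120 per arm also lies close to 30% versus 15% (n = 120.5). The examples concern rehospitalizations and ER visits, not the composite.

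**6. What section 9.4 delivers.** This was simulated with 200,000 runs at true rates of 24% and 15%. The treatment rate is taken from the first 60 treated patients, and N is the larger of 120 and the recalculated value. Two rules were assumed because the plan gives none: a cap on N, and use of the cap if the observed rate reaches the reference control rate.

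| Reference control rate | Cap 181 | Cap 300 | Cap 600 |
|---|---|---|---|
| 30% (implied by the examples) | 50% | 56% | 59% |
| 48% (section 9.2) | 43% | 43% | 43% |
| 24% | 56% | 72% | 82% |

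With reference 30%, an observed 15% (9 of 60) gives only 121 per group, and N rises above 121 in 41% of runs. With reference 48%, N rises in 0.1% of runs.

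**The case against.** The strongest reply is that 24% is not the composite rate. It covers ED visits or readmission only, in revascularized patients, whereas section 8.1.2 provides for patients treated with or without PCI. Section 9.5.1.1 counts any downstream test, and section 9.2 adds death. Events outside an ED visit or readmission could raise the rate, and nothing in the documents excludes 46.5%. This stands as a caveat, which is why power is shown as a range. It does not rescue the claim: section 9.2 does not argue for stand-alone tests, puts the tests at the presentation, and gives no other per-patient figure.

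The rate could also be lower. The published range starts at 20%, and section 9.5.1 words the primary aim as cardiac ED visits. A lower rate makes the shortfall worse.

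Second, 30% is the upper end of the published range in 9.2, so it is not arbitrary. But section 9.4 does not name it, and it differs from the rate used for power.

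Third, section 9.4 could be run with 24%, reaching about 82% power with a cap of 600 per group. That is so, but the section does not say this and its examples contradict it.

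Finally, sections 5 and 9.4 call this a pilot study. That would excuse low power if it were disclosed; section 9.2 claims adequate power instead.

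**Conclusion.** The concern holds. The 48% is a count of events used as a proportion of patients. On the only per-patient rate in the plan, 120 per arm gives about 43% power for a 37.5% reduction, against the 80% or more claimed. The claim would need about 46.5% or more of control patients to have at least one component, nearly twice the figure the plan supports.

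Section 9.4 cannot be carried out unambiguously as written. With the control rate implied by its examples, or with that of section 9.2, it does not restore 80% power if the true rates are 24% and 15%.

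The size rests on a two-sided 0.05 test, no dropout and a 24% composite rate. The mismatch of unit, and the conflict between sections 9.2 and 9.4, do not depend on the 24%.

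**What to change.** - **Section 9.2:** replace 48% with the proportion of patients who have at least one component by day 90. A registry estimate of the composite is preferable, and is needed if stand-alone tests or deaths count; otherwise use 24%. Restate what 120 per arm delivers. At 24% this is about 43% power for a 37.5% reduction, or 80% power for a reduction of about 57%, with a CI half-width of about 10 percentage points.
- **Section 9.6:** state that each patient counts once, with any component scored yes or no.
- **Section 9.4:** name the control rate, make it the same as in 9.2, apply it to the same composite, correct the examples and set a maximum N. With 24%, an observed 10% gives 112 (so 120 is kept), 15% gives 304 per group and 17.5% gives 610 per group.

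The cost is wording in three sections and one registry query. The stated power becomes less favourable. Carrying 24% into 9.4 lets the trial grow: at true rates of 24% and 15%, the mean size per group is 166 (cap 181), 236 (cap 300) or 344 (cap 600). The cap has to be feasible: 600 per group is 1,200 patients, equal to two full years of the roughly 600 AMI discharges a year in section 9.2. Keeping 120 per arm as a pilot is also acceptable if the low power is stated and 9.4 is revised to match.

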9.3. Treatment Assignment Procedures

A computer-generated randomization scheme will be utilized assigning each consecutive patient enrolled to one of the two groups. The randomization scheme is 1:1. Patients and providers are to adhere to the protocol.

9.4. Interim Analyses and Stopping Rules

Due to the uncertainty in proposed rehospitalization rate of the treatment arm, a sample size reestimation (SSR) will be performed after 60 patients have finished the study in the treatment group. The rate will be estimated only for the treatment group, and the sample size will be recalculated using the new calculated rate. The results of this calculation will be the new larger sample size for the study. If the calculation proposes a sample size that is smaller, the original 120 patients per group will be used. No stopping rules are implemented for this pilot study.

As an example, there may be more rehospitalizations and ER visits than expected in the treatment group. If the rehospitalizations and ER visits were 17.5% at 90 days, this would result in the sample size being increased to 181/group. Alternatively, if the rehospitalizations and ER visits in the treatment group were 10%, the sample size required would only be 62/group. If this were to happen, the sample size for the study would be maintained at 120 per group.

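### Section 9.4 re-estimates the sample size from the device arm's rate alone and section 9.6 applies an ordinary chi-square test, so alpha 0.05 is not controlled; the inflation is modest, and the rule lacks a maximum.

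*Combined protocol and SAP*

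**What the plan says.** Section 9.2 sizes the trial at 120 per arm on a composite of ED visits, readmissions and downstream tests, with an expected control rate of 48%. It claims beta below 0.2 and a result that is "statistically significant (at alpha error levels of <0.05) for a 37.5% event reduction". It also gives a registry rate of 24% for ED visit or readmission alone.

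Section 9.4 re-estimates the size once 60 device-arm patients have completed: "The rate will be estimated only for the treatment group, and the sample size will be recalculated using the new calculated rate". If the answer is above 120, "The results of this calculation will be the new larger sample size for the study"; if below, 120 per arm is kept. Its two examples are worded for rehospitalisations and ER visits: 17.5% leads to 181 per group, and 10% would need 62. There are no stopping rules.

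Section 9.6 compares the composite between arms "via Chi square test for categorical data of independent samples".

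The supplied text gives no maximum size, no control rate for the recalculation, and no instruction for an interim device rate that equals or exceeds that control rate. It has no combination test, alpha adjustment or adjusted estimate.

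**The concern.** The final size is a function of unblinded outcomes in one arm. A device rate that is low by chance leaves the trial at 120 per arm and keeps the lucky result at full weight. A rate that is high by chance enlarges the trial and dilutes the bad luck. A chi-square test that treats the size as fixed ignores this, so neither its error rate nor the raw risk difference has its nominal properties.

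A practical problem sits beside the statistical one. The recalculated size grows without limit as the observed device rate approaches the assumed control rate, and beyond that point the formula has no meaning. With no maximum and no rule, someone must improvise after seeing device-arm results.

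**Working it through.** **Inputs.** From section 9.2: alpha 0.05 (taken as two-sided; the text does not say), power 0.80, composite 48% falling by 37.5% to 48% × 0.625 = 30%. From section 9.4: interim at 60 device-arm completers, floor 120 per arm, examples 181 and 62. Assumed, because not stated: control rate in the recalculation 30% or 48%; cap 240 to 600 per arm; at or above control, the size either goes to the cap or stays at 120; the same endpoint is re-estimated and tested.

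**Step 1: reproduce the plan's figures.** With p̄ the mean of the two rates,

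n per arm = [1.96·√(2p̄(1−p̄)) + 0.8416·√(pC(1−pC) + pT(1−pT))]² / (pC − pT)².

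- Section 9.2, 48% vs 30%: n = 115, and power at 120 per arm is 0.820. The claim holds.
- Section 9.4, pC = 30%, pT = 17.5%: (1.1796 + 0.5010)² / 0.125² = 180.8, so 181. With pT = 10%: 61.6, so 62. Both match.
- The same examples give 36 and 22 with a 48% control, and 610 and 112 with a 24% control. Section 9.4 therefore rests on an unstated 30% control rate that appears nowhere in section 9.2 as a control rate. (30% vs 15% gives 120.5.)

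**Step 2: sizes the rule can ask for (30% control).** Interim rates of 20%, 22% and 24% give 293.2, 470.7 and 858.3, so 294, 471 and 859 per arm. (With 60 patients, rates move in steps of 1/60, so 22% and 24% are illustrative.) At 24%, 2 × 859 = 1,718 patients. Section 9.2 counts at least 600 AMI discharges a year, and the study is to last two years: about 1,200 before exclusions and refusals. If the true device rate is 24%, the chance of 18 or more events in 60 (30% or more, no size) is 17.3%.

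**Step 3: operating characteristics under no effect.** Enumerate the interim count X ~ Binomial(60, p), set N = max(120, n) up to the cap, then enumerate the remaining device-arm and all control-arm outcomes and apply the Pearson chi-square without continuity correction. Ranges are over caps of 240 to 600. Errors are in %. Bias is the mean error in the risk difference in percentage points; negative favours the device.

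| Assumed control | True rate, both arms | Fixed 120: two-sided | To cap: two-sided | To cap: device tail | To cap: bias | Stay at 120: two-sided | Stay at 120: device tail | Stay at 120: bias |
|---|---|---|---|---|---|---|---|---|
| 30% | 15% | 5.1 | 4.7–4.8 | 2.7 | −0.6 to −0.4 | 4.7–4.9 | 2.7 | −0.5 to −0.4 |
| 30% | 20% | 5.1 | 5.3 | 2.9–3.2 | −0.7 to −0.4 | 5.6 | 2.9–3.2 | −0.5 to −0.3 |
| 30% | 24% | 5.0 | 5.3–5.5 | 2.9–3.2 | −0.5 to −0.2 | 5.6–6.0 | 2.8–3.1 | +0.1 |
| 30% | 30% | 5.0 | 5.2–5.3 | 2.6–2.8 | −0.1 to 0.0 | 5.0–5.1 | 2.2–2.3 | +0.5 to +0.8 |
| 48% | 30% | 5.0 | 4.6–4.8 | 2.6–2.7 | −0.7 to −0.5 | 4.7–4.9 | 2.6–2.7 | −0.7 to −0.5 |
| 48% | 40% | 5.2 | 5.3–5.4 | 2.9–3.2 | −0.7 to −0.3 | 5.7–6.0 | 2.8–3.1 | −0.2 to 0.0 |
| 48% | 48% | 4.6 | 5.0–5.5 | 2.6–2.9 | −0.2 to 0.0 | 4.8–5.0 | 2.3 | +0.6 to +0.9 |

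Drawing N from the same distribution but independently of the data brings the error back to 4.7–5.2%, so the excess comes mainly from the re-estimation. At the design effect (48% vs 30%), with the size going to the cap, bias is −0.5 to −0.7 points on a true −18.

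**Step 4: a remedy tested.** Combine the z-statistic from the first 60 per arm with that from later patients, with equal weights fixed in advance: z = (z₁ + z₂)/√2. Error is 4.8–5.1% in every null scenario run. With a 400 cap and 48% control, power is 0.927 against 0.930 for the ordinary test at 48% vs 30%, and 0.774 against 0.811 at 48% vs 36%.

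**The case against.** A reader might infer that the rule badly inflates alpha. It does not. The worst two-sided error here is about 6.0%, several null scenarios stay below 5%, and part of the 5.3–5.4% at a 48% control with a true 40% is chi-square discreteness, since a fixed 120 per arm already gives 5.2%.

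A reader might also infer that the estimate is always biased toward the device. The documents do not support that. Keeping 120 is the only fallback that section 9.4 names. If it also applies when the interim rate is at or above control, the bias can run up to about 0.9 points against the device. That reading lowers the device tail in places but gives the highest two-sided error.

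Third, section 9.4's examples concern ED visits and readmissions while the test is on the composite. If the two sections really use different endpoints, their correlation is imperfect and the distortion is smaller than shown.

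All three points stand and limit the size of the claim. Two further defences do not stand. The absence of stopping rules is no answer, because the problem is a data-dependent size, not early stopping. Nor is the pilot label, because section 9.2 claims a specific alpha and power.

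**Conclusion.** The plan claims an alpha that its design does not control, and the recalculation rule is incomplete. Under the assumptions listed, two-sided error runs from about 4.6% to 5.5% if the size goes to the cap and up to about 6.0% if it stays at 120, against about 4.6% to 5.2% for a fixed 120 per arm. The device-favouring tail reaches about 3.2% instead of 2.5%. Bias stays below 1 percentage point: usually toward the device, sometimes against it. The inflation is modest and not universal, and its exact size cannot be settled until the missing elements are written down.

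The missing maximum and the missing no-size rule are defects whatever one thinks of the alpha. Sections 9.2 and 9.4 also need to be reconciled: a 48% composite and a 24% ED/readmission rate in one, an implied 30% control in the other.

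**What to change.** Keep the re-estimation, but test the primary endpoint with a combination of the before-interim and after-interim statistics using weights fixed in advance, and report a matching estimate and confidence interval. State in section 9.4 the maximum size per arm and what happens when the interim device rate is at or above the control rate. Name one endpoint and one control rate, and use them in both 9.2 and 9.4.

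This changes wording only. The cost is power: about 0.3 percentage points at 48% vs 30% and about 4 points at 48% vs 36%, with a cap of 400 per arm.

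Alternatively, re-estimate from the pooled event rate of both arms without using arm labels, keeping the 120 floor and adding a maximum. The planned relative reduction must then be stated, because 9.2 uses 37.5%. The price is that a pooled rate corrects a wrong overall event rate but not an effect smaller than planned, and uncertainty about the device-arm rate is the reason section 9.4 gives for re-estimating.

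### The sample size re-estimation in 9.4 rests on an unstated control rate of about 30% for ED visits and rehospitalizations; 9.2 gives 24% for those events and sizes the trial on another endpoint, and the rule has no maximum

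*Combined protocol and SAP*

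**What the plan says.** Section 9.4 plans one re-estimation, from the treatment-group rate alone. It motivates this with the possibility that "there may be more rehospitalizations and ER visits than expected in the treatment group". It then gives two examples: "If the rehospitalizations and ER visits were 17.5% at 90 days, this would result in the sample size being increased to 181/group", and "if the rehospitalizations and ER visits in the treatment group were 10%, the sample size required would only be 62/group". On the outcome it says "The results of this calculation will be the new larger sample size for the study", with one limit: "If the calculation proposes a sample size that is smaller, the original 120 patients per group will be used". It names no control rate, alpha, power or maximum for this step, and no action if the treatment rate equals or exceeds the control rate.

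Section 9.2 says of the institution's registry that "24% of revascularized AMI patients will present to the ED or will be readmitted within 90 days", and adds that the literature reports 20-30%. It does not size the trial on those events. It moves to a combined endpoint that adds downstream cardiovascular tests and reaches an event rate of 48% on this premise: "Assuming that patients presenting with cardiovascular concern may receive two of the outlined downstream test as they present to the ED and hospital". The 120 per arm is justified by a 37.5% reduction from that 48%, with alpha below 0.05 and beta below 0.2. Section 9.6 applies the chi-square test to the combined endpoint.

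**The concern.** The re-estimation sets the final size of the trial, so its inputs have to be stated and have to match the design. Here the control rate can only be worked out backwards from the examples. The rate that emerges is not the one 9.2 reports for the same events, and the events are not the endpoint that 9.2 sizes or 9.6 tests. Two statisticians running the rule on the same interim data could reach very different sizes: 181 per group with the implied rate, or 610 with the registry rate, for the plan's own 17.5% example.

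The required size also rises without limit as the treatment rate approaches the control rate. With only 60 patients, the observed rate can land close to control by chance, and the rule would then call for a trial that the site cannot enrol.

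**Working it through.** **Inputs.** From 9.2: alpha 0.05, power 80%, 120 per group, 24% (ED visit or readmission), 48% and a 37.5% reduction (combined endpoint), at least 600 AMI discharges a year. From 9.4: treatment rates 17.5% and 10%, sizes 181 and 62, interim at 60 treatment-group completers. From 9.3: 1:1 allocation. Sidedness is not stated; two-sided is assumed.

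**Formula** (chi-square test, pooled variance), with p̄ = (p₁ + p₂)/2:

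n per group = [1.960·√(2p̄(1−p̄)) + 0.842·√(p₁(1−p₁) + p₂(1−p₂))]² / (p₁ − p₂)², rounded up.

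**Step 1. Reproduce the plan's figures.** With p₁ = 0.30 and p₂ = 0.175: p̄ = 0.2375, the roots are 0.6018 and 0.5953, and n = (1.1796 + 0.5010)² / 0.015625 = 180.75, so 181. With p₂ = 0.10: n = 61.6, so 62. Both match. The implied base case, 30% vs 15%, gives 120.5, so 121, next to the planned 120. In steps of 0.05 percentage points, 30.0% is the only control rate that returns both figures exactly under this formula. Allowing one-sided, unpooled, arcsine, continuity-corrected and higher-power variants, with some tolerance on the sizes, the control rate still lies between 28.9% and 31.1%.

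**Step 2. Use the rate 9.2 gives for the same events.** With p₁ = 0.24 and p₂ = 0.175: p̄ = 0.2075, the roots are 0.5735 and 0.5716, and n = (1.1240 + 0.4811)² / 0.004225 = 609.8, so 610. With p₂ = 0.10: 111.8, so 112.

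| Treatment rate | Section 9.4 | Control 30% | Control 24% |
|---|---|---|---|
| 10% | 62 | 62 | 112 |
| 15% | not given | 121 | 304 |
| 17.5% | 181 | 181 | 610 |

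**Step 3. Check 9.2 on its own endpoint.** 0.48 × (1 − 0.375) = 0.30. For 48% vs 30%, n = 114.1, so 115, and 120 per group is sufficient. The size is therefore consistent within 9.2, but for an endpoint other than the one in the 9.4 examples.

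**Step 4. Run the rule without a maximum, against the implied 30%.**

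| Events in 60 | Rate | n per group |
|---|---|---|
| 12 | 20.0% | 294 |
| 13 | 21.7% | 432 |
| 14 | 23.3% | 690 |
| 15 | 25.0% | 1,251 |
| 18 | 30.0% | undefined (division by zero) |
| 21 | 35.0% | 1,377 (treatment arm worse than control) |

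432 per group is 864 patients. 690 per group is 1,380, against 240 planned over one to two years and 2 × 600 = 1,200 AMI discharges in two years.

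**Step 5. How often this happens.** With X ~ Binomial(60, p):
- True rate 15%: P(X ≥ 14) = 5.8%.
- True rate 24% (no effect on the registry rate): P(14 ≤ X ≤ 22) = 59%. Every count in that span gives at least 690 per group, except 18 (6.4%), which gives no answer.

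**The case against.** The strongest reply is that 30% does have a source: it is the top of the literature range in 9.2, and 9.4 offers its figures only as examples in a pilot study. That stands in part. The rate is not invented. But 9.2 never names 30% as the control rate for any calculation, and the examples are the only place from which the control rate of the rule can be recovered.

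A reader might infer that 181 and 62 are arithmetic mistakes. They are not; they are correct for 30%. The fault is an unstated input that conflicts with 9.2.

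A reader might also infer that 9.4 has the direction wrong, because 17.5% lies below the 30% treatment rate implied by 9.2. That compares two endpoints. On ED visits and rehospitalizations, 24% less 37.5% is 15% (0.24 × 0.625), so 17.5% is indeed more than expected. For the same reason, 17.5% or 10% of ED visits and readmissions should not be set against the 48% combined-endpoint rate.

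Finally, the infeasible sizes are not the usual result if the device works as hoped: 5.8% of interims at a true 15%. The 59% applies only if the device has no effect on a 24% rate. Both follow from the rule as written, and a maximum removes both.

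**Conclusion.** The point holds as an inconsistency of inputs between 9.2 and 9.4, together with an unbounded rule, and it must be fixed before the re-estimation is run. The implied control rate is about 30%, against 24% in 9.2 for the same events. That moves the 17.5% example from 181 to 610 per group and the 10% example from 62 to 112. As exemplified, the rule re-sizes the trial for an endpoint that the primary test does not use. With no maximum, 14 events in 60 already ask for more patients than the site discharges in two years.

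The sizes assume a two-sided 5% test, 80% power and the pooled formula; under the variants tried, neither 24% nor 48% returns 181 or 62. That 9.4 survives from an earlier sizing at 30% vs 15% is plausible, but the documents do not say so.

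A reader might infer that the re-estimation biases the chi-square test. Nothing here shows that; the finding concerns the size of the trial and its power. Whether 48% is a per-patient proportion or a count of events is a separate question about 9.2. It has to be settled first, because the corrected rule uses that rate.

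**What to change.** Change 9.4 as follows.

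1. Base the re-estimation on the primary combined endpoint, as the proportion of patients with at least one event. First reconcile its definition: 9.2 adds mortality, 9.5.1 refers to cardiac ED visits, and 9.5.1.1 does neither.
2. Name the fixed control proportion, the same one that 9.2 uses for that endpoint, with a two-sided 5% test and 80% power.
3. State a maximum per group that the site can enrol. State in advance which size applies if the treatment proportion is at or above control: the planned size or the maximum. That is the sponsor's choice.
4. Delete 181 and 62 and recompute. At 48%, treatment rates of 30%, 35% and 40% give 115 (so 120 is kept), 225 and 604 per group. If the sponsor keeps ED visits and rehospitalizations at 24%, then 10%, 15% and 17.5% give 112, 304 and 610; in that case 9.4 should say why it does not use the primary endpoint.

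Possible wording, with brackets to be filled: *After 60 treatment-group patients have completed follow-up, the proportion with at least one primary combined endpoint event is estimated in that group. The size per group is recalculated for a two-sided 5% chi-square test with 80% power against the control proportion in 9.2 ([P]%). It will be neither below the size in 9.2 nor above [N]. If the observed proportion is at or above [P]%, [the planned size / N] is used.*

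**Cost.** Mostly wording, once the rate in 9.2 is settled. A maximum can leave the trial underpowered for a small true effect. As an illustration, with true rates of 24% vs 15%, a floor of 120 and an assumed maximum of 300 that also applies at or above control, simulated power is 72%. Under that same choice the trial grows to 296 per group on average when the device has no effect (24% in both arms); keeping the planned size there would limit that growth. Downstream tests must also be collected for the first 60 treatment-group patients before the re-estimation. This needs a stated procedure, because the Day 90 call in the Schedule of Evaluations does not list them.
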